9. RESEARCH METHODS

9.1 STUDY DESIGN

This is a non-interventional, retrospective, US, multi-site, cohort study based on existing data from medical records of patients with *NRG1* gene fusion-positive solid tumors treated with afatinib or other systemic therapy. Two cohorts of patients will be identified. The first includes any patient with *NRG1* gene fusion-positive solid tumors who has received afatinib in any line of therapy (afatinib cohort) between 01/01/2017 and 03/31/2020. The second includes any patient with *NRG1* gene fusion-positive solid tumors who has not received afatinib in any line of therapy (other systemic therapy cohort) during the same period and no history of afatinib use. Follow-up will include at least 3 months after initiation of afatinib or other systemic therapy, unless a patient died prior to 3 months of follow-up.

In total, up to 120 patients with *NRG1* gene fusion-positive solid tumors will be selected for this study, of whom up to 70 will be afatinib-treated and up to 50 will be treated with other systemic therapy. Study objectives are to describe these patients and calculate the ORR in each group, as well as to estimate PFS, TOT, TTP, OS, DOR, and DOCB along with describing the incidence and severity of AEs among patients in the two cohorts. Data to be collect through this medical chart review include patient demographics, clinical characteristics at the time of diagnosis/initiation of a line of therapy, treatment-related data points (dates of initiation, discontinuation, dosing), AEs occurring during therapy, disease response, date of progression and/or death.

Given the small number of patients targeted for study inclusion and anticipated differences in baseline characteristics between afatinib-treated and patients treated with other systemic therapies, statistical comparisons are not planned. In lieu of statistical comparisons between cohorts, the non-afatinib arm will provide context for interpreting results among those treated with afatinib. Specifically, this context includes what patients with *NRG1* gene fusions not treated with afatinib look like, how they are managed and treated, and what their clinical outcomes look like. The non-afatinib arm will provide a broader understanding of *NRG1* gene fusions among patients with solid tumors

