Data collection is anticipated to begin in the third/fourth quarter of 2020, allowing for a minimum follow-up period of 3 months. All patients are required to have initiated index therapy (i.e., afatinib in any line; other systemic therapy among those without any history of afatinib) between 01/01/2017 and 03/31/2020. As such, the maximum follow-up period is approximately 39 months. The index date is the date of initiation of afatinib or other systemic therapy between 01/01/2017 and 03/31/2020 for the other systemic therapy cohort.

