9.2.1 Provider/Site/Patient Selection

Provider Eligibility

Providers who meet the following criteria will be eligible to participate:

- 1) Are board-certified oncologist/hematologist.
- 2) Have treated/are treating at least one eligible patient with an *NRG1* fusion-positive solid tumor.
- 3) Are able to participate in research approved by an external institutional review board (IRB).
- 4) Agree to participate in data quality assurance/control processes.

Providers will select patients meeting the study eligibility criteria as described below. Providers will be asked to select eligible patients chronologically, starting with the first patient who first initiated any line of afatinib or chemotherapy, on or after 01/01/2017 through 03/31/2020.

Patient Eligibility

Inclusion Criteria:

- Adults, 18 years of age or older, at the time of diagnosis with any solid tumor.
- Confirmed *NRG1* gene fusion in any solid tumor.
- Initiated afatinib or other systemic therapy (in any line of therapy) for treatment of a solid tumor with *NRG1* gene fusion on or after 01/01/2017 through 03/31/2020.

- Followed up for ≥ 3 months after initiation of afatinib or other systemic therapy (unless deceased prior to 3 months of follow-up).

Exclusion Criteria:

- Treatment with any TKI/ErbB-directed therapy other than afatinib

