9.3.2 Outcomes

Demographic and clinical characteristics of patients with *NRG1* gene fusion-positive solid tumors treated with afatinib and of patients with *NRG1* gene fusion-positive solid tumors treated with other systemic therapy will be summarized for each cohort. These variables serve as outcomes in terms of fulfilling study objectives. These variables also serve as covariates to contextualize other study outcomes (e.g., ORR, DOR, DOCB, PFS, TOT, TTP, OS, AEs).

Table 1. Patient demographics and clinical characteristics.

Characteristic	Definition
Sex	Patient sex, as charted
Age(s)	Age at diagnosis of solid tumor and age at initiation of afatinib or other systemic therapy
Region	US census region of patient: Northeast, South, Midwest, West
Race/ethnicity	Race and ethnicity of patient, as charted
Tumor type	Description/classification of primary tumor of patient (e.g., NSCLC, cholangiocarcinoma, pancreatic cancer)
ECOG PS	ECOG PS of patient at initiation of afatinib or other systemic therapy
Comorbidities	Comorbidities present at initiation of afatinib or other systemic therapy, following Charlson comorbidity index
Stage	Stage of tumor at initiation of afatinib or other systemic therapy
NRG1 results	Date of NRG1 gene fusion test; laboratory performing test (e.g., academic, reference, in-house lab; name of lab); NRG1 gene fusion partner
Other biomarkers	Tumor-specific biomarkers tested and their results (e.g., MSI/MMR, EGFR, HER2)

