DOR	Duration of response will be calculated as the time from initial response (for any patient with a complete or partial response initially) until the earliest of either disease progression or death. Patients who discontinue therapy due to a reason other than progression will be censored on the date of discontinuation. Patients still on therapy at the time of data cut-off will be censored on their last visit date.
TOT	Time from initiation of a line of therapy until discontinuation for any reason; patients on therapy at the time of data cut-off will be censored on the last date of treatment.
TTP	Time from initiation of a line of therapy until discontinuation due to disease progression; patients on therapy or those who discontinued due to a reason other than disease progression will be censored on the last date of treatment.

PFS	Time from initiation of a line of therapy until disease progression or death; patients on therapy at the time of data cut-off will be censored on the last date of treatment. Patients who discontinue a line of therapy for a reason other than disease progression but who subsequently die prior to the receipt of any other therapy will be considered an event on the date of death.
OS	Time from initiation of any therapy in the metastatic setting until death; patients alive at the time of data cut-off will be censored on the last date the patient was seen by the provider/clinic.
AE	An adverse event is defined as any untoward medical occurrence in a patient administered a medicinal product and which does not necessarily have a causal relationship with this treatment. AEs from a prepopulated list (including “other, please specify”) during each line of therapy will be indicated by providers. The number and proportion of patients experiencing each AE reported during afatinib or other systemic therapy will be reported. See Section 11.1 and Table 3 for further details.

In addition to TOT, to further characterize treatment patterns for those treated with afatinib and those treated with other systemic therapy, the following will be collected (and calculated based on the collected data):

- Treatment history (i.e., regimens, duration, number of cycles, sequence)
- Starting dose of afatinib or other systemic therapy
- Dose modifications of afatinib or other systemic therapy (i.e., dose reductions and their timing, dose increases and their timing, dose delays and their duration and timing)

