9.7 DATA ANALYSIS

Demographic and clinical characteristics will be reported by descriptive analyses including counts and frequencies for dichotomous and categorical variables, while measures of centrality (mean, median) and spread (min, max, standard deviation, interquartile range, as appropriate) will be used for continuous variables. These characteristics will be described at the time of initial diagnosis of advanced/metastatic disease and at the time of initiation of each line of therapy received, for the afatinib cohort and separately for the other systemic therapy cohort. No statistical comparisons will be made across these two cohorts in terms of demographic, clinical characteristics, and clinical outcomes.

The calculations for all outcomes (e.g., ORR, DOR, DOCB, TOT, TTP, PFS, OS) are defined in **Table 2** in Section **9.3.2 Outcomes**. For disease response, the point estimate for ORR and associated 95% confidence interval (CI) will be calculated for initial response to index therapy (i.e., afatinib or other systemic therapy) and best response to index therapy, for each cohort. ORR will be reported among subgroups within each of the treatment cohorts, by tumor type and line of therapy. The Kaplan-Meier method will be used to estimate time-to-event outcomes (DOR, DOCB, TOT, TTP, PFS, and OS) to account for any right-censoring (e.g., patient had not discontinued therapy, patient had not progressed, or died). Time-to-event outcomes will be described for each of the two treatment cohorts and in subgroups within the two treatment cohorts, according to solid tumor and line of therapy. All study outcomes will be reported separately for those treated with afatinib monotherapy. In the event an outcome cannot be assessed for a given patient, that patient would be omitted from assessment of that outcome; reason for omission in a given outcome assessment will be reported.

Cumulative incidence, severity, and timing of AEs during the index therapy will be summarized and displayed in number/percentage form for each of the treatment cohorts, separately. All safety endpoints will be analyzed descriptively. AE reporting is summarized in Section **11 Management and Reporting of Adverse Events/Adverse Reactions**.

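### Table 2 does not tie the start of OS to the index date; on one of three possible readings, later-line patients inflate OS

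*Combined protocol and SAP*

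**What the plan says.** Section 9.1 sets one reference date: "The index date is the date of initiation of afatinib or other systemic therapy between 01/01/2017 and 03/31/2020". The afatinib cohort is any patient "who has received afatinib in any line of therapy (afatinib cohort) between 01/01/2017 and 03/31/2020", and the inclusion criterion in Section 9.2.1 reads "Initiated afatinib or other systemic therapy (in any line of therapy) for treatment of a solid tumor", so the index therapy may be a first or a later line. Sections 9.1 and 9.2.1 count the required three months of follow-up from that initiation.

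Table 2 in Section 9.3.2 starts TOT, TTP and PFS at a line of therapy; PFS, for example, is "Time from initiation of a line of therapy until disease progression or death". OS alone has a different start: "Time from initiation of any therapy in the metastatic setting until death".

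Section 9.7 refers all outcome calculations to Table 2. It plans Kaplan-Meier to "estimate time-to-event outcomes (DOR, DOCB, TOT, TTP, PFS, and OS) to account for any right-censoring", and does not mention delayed entry. Time-to-event outcomes are reported per cohort and "in subgroups within the two treatment cohorts, according to solid tumor and line of therapy".

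Metastatic disease is not an eligibility condition. Table 1 records "Stage of tumor at initiation of afatinib or other systemic therapy". Annex 1 lists no stand-alone document that could settle the OS wording, and Sections 9.9 and 9.12 do not discuss it.

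**The concern.** OS in each cohort is objective 4 (Section 8), and Section 7 says the data may be used in label-expansion requests. A survival estimate needs one unambiguous time zero. Here the governing table uses a start that differs from the index date and from the other outcomes in the same table.

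The reading that matters most is the first metastatic therapy. A patient enters the cohort only by reaching the index therapy. If that was a second or later metastatic line, the time between first metastatic therapy and index cannot contain a death, because anyone who died in it is not in the cohort. Counting that time as survival raises the curve. The error would sit inside each cohort's own estimate, so the absence of a planned comparison does not remove it, and the Kaplan-Meier confidence interval would not show it.

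**Working it through.** The plan states no OS estimate, event count or later-line share, so it has no figure of its own to reproduce. The check has two parts.

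**1. The three readings of the OS start**

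| Reading | Patient indexed in a later metastatic line | Consequence |
|---|---|---|
| First metastatic therapy | Clock starts before index | Pre-index time is event-free by design; OS is overstated without delayed entry |
| Index therapy, whichever line | Clock starts at index | No such bias |
| Each line | Several clocks | No such bias, but no unique time zero for a patient with several lines |

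A patient indexed before metastatic disease is a separate case. On the first-metastatic-therapy reading the clock starts after index. If the patient never receives therapy in the metastatic setting, OS is undefined.

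**2. Size on the first-metastatic-therapy reading (all inputs assumed)**

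- *T*, survival from index: exponential, median 10 months, so rate λ = ln 2 / 10 and 12-month OS = exp(−12λ) = 43.5%.
- *L*, lag from first metastatic therapy to index: gamma with shape 4 and mean 3, 6 or 12 months for later-line patients, independent of *T*; zero for first-line patients.
- *q*, share of enrolled patients who are later line: 10%, 25% or 50%.

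Reported OS time is *L* + *T*, so the reported curve is S(t) = (1 − q)·exp(−λt) + q·P(L + T > t). Solving S(t) = 0.5 gives these reported medians in months, where 10.0 is the value from index:

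| Later-line share | Mean lag 3 | Mean lag 6 | Mean lag 12 |
|---|---|---|---|
| 0% | 10.0 | 10.0 | 10.0 |
| 10% | 10.3 | 10.7 | 11.3 |
| 25% | 10.8 | 11.8 | 13.5 |
| 50% | 11.6 | 13.5 | 17.1 |
| 100% (later-line subgroup) | 13.1 | 16.3 | 22.8 |

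One cell in full: with q = 50% and mean lag 6, at t = 13.46 the first-line part is exp(−13.46λ) = 0.393 and the later-line part is 0.607; 0.5 × 0.393 + 0.5 × 0.607 = 0.500. In the 50% row the reported 12-month OS is 49%, 55% and 65%, against 43.5% from index.

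Share and lag are linked, because a long lag leaves fewer survivors to enrol. Suppose median survival is 10 months from first metastatic therapy and half of patients are destined for a later line but must survive to reach it. The enrolled later-line share then falls to 45%, 40% and 32% for mean lags of 3, 6 and 12 months, and the reported median is 11.4, 12.5 and 13.8. Survival from index is still 10.0. The cells that combine a long lag with a high share are therefore not typical.

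A second set of assumptions gave the same direction: exponential lag, censoring uniform over 3 to 42 months from index, medians from index of 8 to 18 months, later-line shares of 25% to 75%, and mean lags of 4 to 12 months. The reported median rose by 1.2 to 11.2 months.

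For scale, with n = 70 and no censoring, the sampling SD of a 10-month exponential median is about 1.7 months. The 25% share with 3-month lag (10.8 − 10.0 = 0.8) is about half an SD; the 50% share with 6-month lag (13.5 − 10.0 = 3.5) is about two.

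**The case against.** The strongest reply is that the text says *any*, not *first*. Elsewhere in Sections 9.1 and 9.2.1, *any line* describes the index therapy; follow-up is counted from its initiation; and Section 9.7 reports outcomes by line of therapy, which fits a clock starting at that line. If OS starts at the index therapy given in the metastatic setting, the bias is zero. This stands as a possible reading. It does not close the matter, because nothing in the documents states it and Table 2 words OS differently from its neighbours.

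Three further objections stand in part.

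- Survival from first metastatic therapy and survival from index are different quantities. They share a 10-month benchmark above only because the hazard is constant and the lag independent. If risk changes after earlier lines fail, part of the gap reflects a different time origin rather than bias.
- The upward direction is not general. Patients indexed before metastatic disease have a late or undefined clock, which can act the other way.
- Index-date OS does not remove every form of guaranteed survival. Section 9.2.1 requires a confirmed fusion but sets no rule that the test precede index.

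It can also be said that the study is descriptive and already plans subgroups by line. That lowers the severity but does not remove the point. The cohort estimate is still reported, and on the first-therapy reading every patient with earlier metastatic therapy in a later-line subgroup carries the extra time.

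**Conclusion.** The firm defect is an OS start that is not tied to the index date and has at least three readings. The overstatement is conditional: it needs the first-metastatic-therapy reading and patients indexed in a later metastatic line. A reader might infer that the planned OS is biased upward as it stands. The documents do not support that, because the wording also admits the index therapy, where the bias is zero, and because the later-line share is not given.

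The size cannot be derived from the documents. It is zero if all index therapies are first line. Under the assumptions shown, the reported median would be 10.3 to 11.3 months at a 10% later-line share and 11.6 to 17.1 at 50%, against 10 from index. The range runs from negligible to larger than sampling error. On that reading both cohorts can be affected, since both admit any line; the documents do not show which would be affected more.

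This should be fixed, preferably at protocol finalization and before data collection.

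**What to change.** - In Table 2, define OS in both cohorts as time from the index date (initiation of index therapy) to death, keeping the existing censoring rule.
- In Section 9.1, state which line is index for a non-afatinib patient with several lines in the window; the current text leaves this open.
- In Section 9.7, report OS by stage at initiation (metastatic or not), with patients of unknown stage shown separately, since Section 9.4 allows non-required items to be missing. Which group is the headline is the sponsor's choice. The split matters because pooling can itself move the median: if 10% or 20% of patients were non-metastatic with an assumed median of 40 months, solving (1 − q)·0.5^(t/10) + q·0.5^(t/40) = 0.5 gives 11.1 or 12.4 months instead of 10.0.
- If OS from first metastatic therapy is also wanted, report it as a secondary Kaplan-Meier estimate with delayed entry at the index date. State the assumption that entry time is independent of survival; this may fail if starting a later line follows progression.

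The cost is a few sentences and the matching program. Treatment sequence, initiation dates and stage at initiation are already to be abstracted (Sections 9.1 and 9.3.2). The downside is that reported OS for later-line patients becomes shorter than under the first-therapy reading. The secondary estimate is also less stable: in simulations with n = 70 and a 6-month mean lag, the SD of its median was 2.0, 2.3 and 3.0 months when 50%, 25% and 10% of patients were first line.

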9.4 DATA SOURCES

All study data will be entered by the investigators into the eCRF. The eCRF captures data for each of the study variables described in **Section 9.3 - Variables**. The eCRF is designed to allow providers to efficiently move through the patient chart or EMR based on the journey of the patient through the course of disease. The eCRF conforms to the rules and regulations of the Health Insurance Portability and Accountability Act (HIPAA) of 1996 governing the abstraction and storage of protected health information (PHI).

De-identified, patient-level data will be obtained from providers in the [REDACTED] [REDACTED] who will complete an electronic case report form (eCRF) for eligible patients. [REDACTED]

[REDACTED] will recruit providers from [REDACTED] to participate. [REDACTED] is a community of over 7,000 oncologists, hematologists and urologists from across the U.S., with varying levels of time in practice, from practices both within and outside of group purchasing organizations. A subset of this group (~800) participates in retrospective observational research studies. All provider participation in the study is voluntary.

To be eligible to participate, providers must have treated at least one patient meeting the study eligibility criteria, be able to participate in research approved by an external institutional review board (IRB), and agree to participate in data quality control processes. No provider at practices that require local IRB approval at the practice will be eligible to participate. A waiver of obtaining patient consent will be sought for the study. No protected health information (PHI) beyond dates of diagnosis, treatments, and outcomes will be collected.

Providers will abstract demographic-, clinical-, and treatment- related data as available from the patient's electronic health record (EHR), starting from the time of primary malignancy diagnosis through the last date of follow-up with the patient or death. Providers will complete an eCRF for all eligible patients and will begin data abstraction beginning with the first eligible patients and select consecutive patients moving forward in time. Data elements that are required are specified in the study inclusion/exclusion criteria; non-required data elements may be missing/unknown. Providers may abstract data into the eCRF for both patients they personally managed/treated or those managed/treated by other providers within their practice.

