9.9 LIMITATIONS OF THE RESEARCH METHODS

The limitations of this approach include provider selection bias, patient selection bias, and the lack of source document verification. Regarding bias, only providers who meet the study eligibility requirements and who volunteer to participate in the research study are known; therefore, the representativeness of the providers to all oncologists in the U.S. cannot be verified directly. Additionally, providers will select the patients meeting study eligibility criteria, so they may not include all potentially eligible patients. As such, the representativeness of the patient sample to all patients in the U.S. or in the population of patients within the [REDACTED] also cannot be verified. Source document verification cannot be performed by [REDACTED] however, quality assessment/control procedures to minimize misclassification errors are described in **Section 9.8 – Quality Control**.

- 1) As an exploratory, retrospective, non-randomized study with up to 70 and up to 50 patients per cohort (respectively), post-hoc propensity score matching cannot be conducted and unadjusted/crude comparisons between the two cohorts cannot be made as underlying demographic/clinical characteristics may exist between the cohort. Therefore, statistical comparisons of outcomes between the two cohorts cannot be made.
- 2) Not all patient characteristics will be included in the data collection (e.g., income and other variables that may influence provider-prescribing behavior or treatment decisions) and cannot be accounted for in the descriptive analyses.
- 3) Loss to follow-up during the study period may occur if patients transfer care to other providers and centers. As such, treatments, visits, and outcomes occurring after the date of last visit may be missing.
- 4) Treatment patterns reflected in the study represent only the practices of providers who have agreed to participate, and may vary from non-responding providers, i.e., those who refused study participation or who were unresponsive to the screening invitation. No data is available to describe non-responders.
- 5) This study employs purposive sampling that selects providers and patients based on pre-specified selection criteria and hence this may not be representative of all patients diagnosed with *NRG1* gene fusion-positive solid tumors treated with the drugs of interest or representative of all providers treating these types of patients.

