10 PROTECTION OF HUMAN SUBJECTS

Individual patient medical information obtained as a result of this study is considered confidential and disclosure to third parties is prohibited. All study materials including the research protocol and paper-version of the eCRF will be reviewed by a central IRB prior to any data abstraction including field-testing of the eCRF. A waiver of HIPAA authorization for use of PHI will be requested from the IRB since the following three requirements will be met:

1. The use or disclosure of the PHI involves no more than minimal risk to the individuals, based on the following elements:
 - a. An adequate plan to protect identifiers from improper use and disclosure;
 - b. An adequate plan to destroy the identifiers at the earliest opportunity consistent with conduct of the research (unless there is a health or research justification for retaining the identifiers, or such retention is otherwise required by law); and
 - c. Adequate written assurances that the PHI will not be reused or redislosed to any other person or entity, except as required by law, for authorized oversight of the research project, or for other research for which the use or disclosure of PHI would be permitted by HIPAA.
2. The research could not be practicably conducted without access to and use of the PHI; and
3. The research could not practicably be conducted without the waiver.

Providers are required to be able to participate in research covered by a central IRB. At all times, patients' PHI will be kept confidential in accordance with HIPAA. The eCRF will not capture any data related to the patient's name, full date of birth, social security number, health insurance plan number, medical record number, or other such PHI. However, date of disease diagnosis, date(s) of treatment(s) administered (including dates of dose changes), date of the development of health states of interest (i.e., SAEs/FAEs, disease progression), and date of death (if available) will be collected in the eCRF. These items are considered PHI under HIPAA. All study results will be reported in aggregate; however, an anonymized patient-level dataset will be delivered to BI at the completion of the analytic cohort build.

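### OS follows deaths and survivors to different dates, so the Kaplan-Meier censoring is informative, in a direction that the plan cannot determine

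*Combined protocol and SAP*

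**What the plan says.** Table 2 in section 9.3.2 defines OS as "Time from initiation of any therapy in the metastatic setting until death". It sets no limit on how long after the last clinic contact a death may fall. For survivors, "patients alive at the time of data cut-off will be censored on the last date the patient was seen by the provider/clinic".

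Section 9.4 has providers abstract each record "through the last date of follow-up with the patient or death", so a death later than the last visit can be entered. Section 10 says that "date of death (if available) will be collected in the eCRF". Limitation 3 in section 9.9 reads "Loss to follow-up during the study period may occur if patients transfer care to other providers and centers" and adds that "treatments, visits, and outcomes occurring after the date of last visit may be missing".

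Section 9.7 applies Kaplan-Meier to OS and to the other time-to-event outcomes. The documents describe no date last known alive, no check of vital status at cut-off, and no rule for patients whose status is unknown. Item 10.8 of the ENCePP checklist (Annex 2) marks sensitivity analyses as described in section 9.7, but that section has none on OS censoring.

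**The concern.** Kaplan-Meier needs censoring to be unrelated to the time of death. Here, a patient who stops attending and whose death reaches the chart stays in the risk set until that death. A patient who stops attending and lives is taken out at the last visit. After the last visit, the risk set keeps only those who die on record, which overstates the late hazard.

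A second mechanism pulls the other way. If a death never reaches the chart, the patient presumably passes as alive and is censored at the last visit. If such patients are mostly those about to die, OS is overstated.

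OS is objective 4. Section 7 says that the data may support label-expansion requests, and section 9.1 uses the second cohort as context for the afatinib results. A reader of the OS medians would need to know which mechanism dominates.

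**Working it through.** **Nothing to reproduce.** The documents give no OS median, visit interval, loss rate or death-capture rate. The check applies the written rule to assumed values.

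**Inputs.**
- From the documents: index dates "between 01/01/2017 and 03/31/2020. As such, the maximum follow-up period is approximately 39 months"; data collection in Q3/Q4 2020; up to 70 afatinib patients.
- Assumed: cut-off about 1 October 2020, which gives 6 to 45 months of potential follow-up (the protocol's 39 months is the length of the index window); uniform index dates; clock started at the index date; exponential OS; visits every 1 to 3 months; rates of leaving and of death capture as stated below.

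**Step 1: hand check, true median 18 months, no leavers.**
- Hazard λ = ln 2/18 = 0.0385 per month.
- Proportion alive at cut-off: S = (e^(−6λ) − e^(−45λ))/(39λ) = (0.794 − 0.177)/1.502 = 0.411. Proportion dead: D = 0.589.
- Person-time per patient: D/λ = 15.30 months.
- With visits every v months, the rule removes on average v/2 months from each survivor and nothing from a recorded death. If a share m of deaths is missed, those patients are also cut back to the last visit. An exponential fit then gives:

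  median ≈ ln 2 × [15.30 − (S + mD)·v/2] / [D(1 − m)]

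| v (months) | m = 0 | m = 5% | m = 10% | m = 20% |
|---|---|---|---|---|
| 1 | 17.8 | 18.7 | 19.7 | 22.1 |
| 3 | 17.3 | 18.1 | 19.1 | 21.3 |

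The two effects cancel at m = (S·v/2)/(15.30 − D·v/2). This is 0.205/15.01 = 1.4% for monthly visits and 0.616/14.42 = 4.3% for three-monthly visits. With no leavers, a few per cent of missed deaths is enough to change the sign.

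**Step 2: Kaplan-Meier simulation of the written rule (300,000 patients per scenario).**
- All deaths recorded, no leavers, visits every 1, 2 and 3 months: 17.8, 17.6 and 17.4 against 18; 11.9, 11.9 and 11.7 against 12; 23.6, 23.4 and 23.2 against 24. The shift is 0.6 to 3.3%. Censoring survivors at cut-off instead gives 18.0 to 18.1 for the 18-month case.
- Transfer of 10, 20 and 30% per year, all later deaths recorded, monthly visits, true 18: 17.0, 16.4 and 15.7, or 5, 9 and 13% low. 24-month OS falls to 0.368, 0.342 and 0.316 against a true 0.397.
- Same transfer rates, unrelated to prognosis, no death recorded after transfer: 17.8, 17.8 and 17.6. The bias almost vanishes.
- Deaths missed among all patients, no transfers, monthly visits: 18.7, 19.8 and 22.1 for 5, 10 and 20% missed. With three-monthly visits, 5% missed gives 18.3.
- Patients leaving within 3 months before death, those deaths missed, plus 10% transfer per year: 19.6, 21.7 and 24.7 for 10, 20 and 30% of patients.

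**Step 3: monthly leaving rates (200,000 patients, two-monthly visits, 80% of later deaths learned).** With 2% and 4% leaving per month, the median is about 11.3 and 10.9 against 12, and about 16.2 and 15.2 against 18. The relative shifts are 0.7/12 = 6%, 1.1/12 = 9%, 1.8/18 = 10% and 2.8/18 = 16%.

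**Step 4: sampling error.** Expected deaths with 70 patients: 70 × 0.589 = 41. An approximate 95% interval for an 18-month median is 18 × exp(±1.96/√41), or about 13 to 24 months. The largest downward shift above is 2.8 months, inside that interval. Only the most extreme missed-death scenario (24.7) falls outside it.

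**The case against.** A reader might infer that OS is simply biased downward. The documents do not support that. Section 9.9 warns that outcomes after the last visit may be missing, and section 10 collects the date of death only where available. The text under Table 2 expressly provides for a date of death only where death is the reason for stopping treatment. Missed deaths can cancel or reverse the effect, as the working shows. This part of the objection stands, and the direction has to be conditional.

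A reader might also infer that the rule distorts one cohort against the other, because visit spacing and departure could differ between an oral drug and other systemic therapy. No visit schedule or loss rate is given for either cohort, and sections 9.1, 9.5, 9.7 and 9.9 rule out statistical comparison. That step is speculation.

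The simulation also starts the clock at the index date, whereas Table 2 starts it at any therapy in the metastatic setting. A later-line patient must survive to the index date to be included, which pushes estimated OS upward and is not modelled here. The figures therefore isolate the effect of the censoring rule and do not give the net error in the reported OS.

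Finally, the study is descriptive and small, and sampling error mostly exceeds the shift. That limits the weight of the point but does not answer it: a confidence interval does not cover systematic error. None of these objections supplies a common end of follow-up for deaths and survivors.

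**Conclusion.** The point holds in conditional form. The OS rule ends follow-up on different dates for deaths and survivors, so the censoring is informative.

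- Later deaths well recorded: OS is understated, by about 1 to 3% of the median with no leavers, and by about 5 to 16% with 10 to 30% transfer per year and full capture, or 2 to 4% leaving per month and 80% capture.
- Deaths missed: the understatement shrinks or turns into overstatement, to about 19.8 against a true 18 months when 10% of deaths are missed with monthly visits and no transfers.

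All rates, the exponential shape and the cut-off date are assumptions. The documents give no means of choosing between the cases, so neither a firm downward bias nor a difference in bias between the cohorts can be asserted. The more basic gap is that a patient who has left the practice may have unknown vital status, and the plan does not say how that patient is classified.

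**What to change.** In the OS row of Table 2 and in the eCRF:

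1. Fix one calendar cut-off date, and record vital status at that date as alive, dead or unknown.
2. Record the date last known alive from any chart source (visit, telephone contact, laboratory result, refill, outside letter). Censor patients not known to have died at that date, no later than the cut-off, in place of the last date seen.
3. In section 9.7, add one sensitivity Kaplan-Meier estimate in which deaths more than a pre-set interval after the last chart contact (for example 90 days) are censored at that contact.
4. Report both medians and the number of patients of unknown vital status in each cohort, and state that the correction is partial.

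The correction is partial because later deaths still count while some survivors stop at their last contact, and because a missed death stays missed unless the vital-status question uncovers it. In the simulated case with a true median of 18 months, 4% leaving per month and 80% of later deaths learned, the written rule gives 15.2. Any-source contact dates raise it to 15.5 and the 90-day rule to about 16.1. The 90-day rule with in-care survivors censored at cut-off gives 16.4. With a true median of 12 months, the 90-day rule hardly moves the median. The value lies in showing readers how far OS depends on the rule.

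The cost is one or two eCRF fields, a slightly longer chart search for patients no longer attending, and one extra analysis run.
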